## 8. EFFICACY ASSESSMENT

### 8.1. Specification of Efficacy Parameters

- **Primary outcome:** the number of COPD exacerbations due to infectious episodes diagnosed by the clinician in charge.
- **Secondary outcomes:**
  - Rate of COPD exacerbations per patient included in the study.
  - Decrease in the severity of the COPD exacerbations.
  - Time elapsed between the start of the treatment and the first COPD exacerbation.
  - Use of drugs (antibiotics, corticosteroids, etc).
  - Number of medical consultations due to COPD exacerbations.
  - Number of hospitalizations due to COPD exacerbations.
  - Days of hospitalization due to COPD exacerbations.
  - Number of visits to the Emergency Department resulting or not in hospitalization.
  - Health-related quality of life, as determined by an adapted version of the specific CAT test.
  - Ratio between the number of COPD exacerbations and the healthcare expenditure resulting from resource consumption during episodes of COPD exacerbations occurring during the trial period.

- Variations (change between the baseline level and months 0, 3, 6, and 12, as well as in comparison with the placebo) in the immunological parameters described in page 63.
- Safety outcomes:
  - ~ Overall rate, severity, and relationship of any adverse event per administration and patient.
  - ~ Assessment of local tolerability (tissular reactions in the administration site).
  - ~ Changes in standard laboratory parameters (serum chemistry and hematology).

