### **10. STATISTICS**

#### **10.1. Description of the Statistical Methods to be Used, Including the Schedule of any Planned Interim Analysis**

The study analysis will be performed after the database lock. The intention-to-treat (ITT) population will be composed of subjects who took at least one dose of the trial medication. The analysis will be performed on both the ITT and per-protocol populations.

The randomization will be evaluated by comparing the baseline variables (month 0) in both study groups according to the Consolidated Standards of Reporting Trials (CONSORT) due to their clinical relevance. Qualitative variables will be reported together with their frequency distribution, and quantitative variables will be reported together with their mean and standard deviation, or, in case of asymmetry, with their median and interquartile range. If confounding is detected, the effects will be adjusted with the potentially confounding variables using the appropriate model adjustments.

The following variables will be analyzed to determine whether they follow a normal distribution: number of exacerbations, duration of the episodes, need for antibiotic therapy, number of hospital admissions, duration of the hospital admissions, immunological outcomes described in the trial design (page 67), quality of life, and direct costs.

These variables will be described together with their mean and standard deviation, or, in case of asymmetry, with their median and interquartile range. Differences between the means will be analyzed using Student's T test in the case of variables with a normal distribution and Mood's median test in the case of variables without a normal distribution. The absolute effect (difference in estimators) and its precision will be estimated with a 95% confidence interval (CI) in all cases.

The rate of exacerbations per patient and the severity of these exacerbations will be compared using the chi-square test or Fisher's exact test. The relative risks will be estimated together with their 95% CI. The number needed to treat (NNT) or number of events prevented per treatment will be estimated.

The rate of episodes occurred over time will be calculated, and the hazards ratio (HR) will be estimated together with its 95% CI following a Cox proportional-hazards model. The NNT (number of patients that need to be treated to avoid an event) will also be estimated.

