To compare the change in the immunological variables described in the trial design (page 67) at 0, 3, 6, 12, and 18 months, an analysis of covariance will be performed, estimating the mean difference over time in both study groups.

The cost-benefit ratios in the study groups will be estimated together with their 95% CI, and compared using non-parametric tests.

The safety variables will be compared using the chi-square test in the case of qualitative variables or Student's T test in the case of quantitative variables whenever they meet parametric assumptions, or using non-parametric test in the opposite case.

The statistical software that will be used is STATA 11.

---

**10.2. Number of Anticipated Subjects and Rationale. Calculation Method Used for Determining the Sample Size and Data Used for Such Purpose**

The calculation of the sample size is based on the efficacy measured based on the decrease in the number of episodes of COPD exacerbations during the 12-month treatment period of the trial per subject.

The ratio of subjects to be distributed among the active treatment and placebo groups will be 1:1.

We estimate that subjects from group I (active treatment with the bacterial vaccine) will achieve a 60% decrease in their number of COPD exacerbations compared with a 30% decrease among those of group II (placebo). With an alpha error of 0.05 and a beta error of 0.2, and assuming a dropout rate of 20-25%, the number of subjects to be recruited would be 90 per study group, with an overall total of 180 trial subjects.

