6.1.2. Secondary outcomes

- ★ Decrease in the rate of COPD exacerbations per study group at 12 months (end of the trial treatment) and 6 months after the trial's termination (follow-up).
- ★ Decrease in the severity of the COPD exacerbations. The severity of the exacerbations will be measured based on the consumption of healthcare resources (i.e., visits to the Emergency Department, hospitalizations, or consultations), as follows:
 - ICU hospitalization: 4 points.
 - Standard hospitalization: 3 points.
 - Emergency Department visit: 2 points
 - Consultation involving a change in the patient's usual treatment: 1 point.
- ★ Time elapsed between the start of the treatment and the first COPD exacerbation
- ★ Use of drugs (antibiotics, corticosteroids, etc). Drug consumption will be scored as follows:
 - Use of antibiotics: 1 point.
 - Use of inhaled corticosteroids: 2 points.
 - Use of systemic corticosteroids: 3 points.
 - Use of oxygen therapy: 4 points.
 - Use of mechanical ventilation: 5 points.
- ★ Number of hospitalizations due to COPD exacerbations.
- ★ Days of hospitalization due to COPD exacerbations.
- ★ Number of visits to the Emergency Room.
- ★ Number of unscheduled medical consultations due to COPD exacerbations.
- ★ Health-related quality of life, as determined by an adapted version of the specific CAT test.
- ★ Healthcare expenditure resulting from resource consumption during episodes of COPD exacerbations occurring during the trial period.
- ★ Variations (change between the baseline level and months 0, 3, 6, and 12, as well as in comparison with the placebo) in the following immunological parameters in the patients participating in the immunological substudy (N = 60) and/or those of the subgroup of the induced sputum study (N = 20) (between month 0 prior to the administration of the vaccine and month 12).

In the case of patients participating in the IMMUNOLOGICAL SUBSTUDY (n = 60), changes in the below parameters will also be assessed during the randomization visit (visit 1) and the visits corresponding to months 3, 6, and 12:

- The specific humoral response [REDACTED]
- The in vitro proliferative response of specific T cells [REDACTED]

In a subgroup of patients (n = 20) selected from the group of patients participating in the immunological substudy (n = 60), the following parameters will also be evaluated in samples of induced sputum at month 0 (visit 1) and month 12:

- ★ IgA response to Bactek antigens assessed using ELISA technique.

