7.4.2. Secondary Efficacy Analysis

The following variables will be analyzed to determine whether they follow a normal distribution: number of exacerbations, duration of the episodes, need for antibiotic therapy, number of hospital admissions, duration of the hospital admissions, immunological outcomes described in the trial design, quality of life, and direct costs.

These variables will be described together with their mean and standard deviation, or, in case of asymmetry, with their median and interquartile range. Differences between the means will be analyzed using Student's T test in the case of variables with a normal distribution and Mood's median test in the case of variables without a normal distribution. The absolute effect (difference in estimators) and its precision will be estimated with a 95% confidence interval (CI) in all cases.

The appearance of the first exacerbation will be studied at 3, 6, 12 months and whole study in the intention to treat (ITT) and per protocol (PP) sets and these same limits will be studied in the moderate and severe COPD populations. The appearance of any exacerbation at 3, 6, 12 months and whole study will be studied in the ITT and PP sets.

Number of exacerbations will be studied in the mild, moderate and severe COPD populations at 3, 6, 12 months and whole study. Number of exacerbations in the ITT and PP sets will be studied at 3, 6, and 12 months.

To compare the change in the immunological variables described in the trial design at 0, 3, 6, 12, and 18 months, an analysis of covariance will be performed, estimating the mean difference over time in both study groups.

The cost-benefit ratios in the study groups will be estimated together with their 95% CI, and compared using non-parametric tests.

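### Protocol 8.1 defines the health-economic secondary outcome as exacerbations divided by their own cost, against the plain expenditure named elsewhere, and that ratio cannot register savings from avoided events at unchanged cost per event

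*Protocol*

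**What the plan says.** Two definitions of the same secondary outcome are in force.

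- Protocol 8.1 lists a "Ratio between the number of COPD exacerbations and the healthcare expenditure resulting from resource consumption during episodes of COPD exacerbations".
- SAP 6.1.2 lists "Healthcare expenditure resulting from resource consumption during episodes of COPD exacerbations occurring during the trial period". Protocol 4.1, Protocol 5.1 and SAP 3.2 use the same wording, with no ratio.

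Two analyses touch on cost.

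- The variables to be checked for normality and compared between arms in Protocol 10.1 end with "quality of life, and direct costs"; SAP 7.4.2 repeats the list. Normally distributed variables get Student's t test and the others Mood's median test. SAP 7.4.2 adds: "The absolute effect (difference in estimators) and its precision will be estimated with a 95% confidence interval (CI) in all cases". Protocol 10.1 says the same.
- Separately, SAP 7.4.2 states: "The cost-benefit ratios in the study groups will be estimated together with their 95% CI, and compared using non-parametric tests". The statistics section of the protocol has the same sentence. Neither document says what is divided by what, whether the ratio is formed per patient or per group, or how a patient with no exacerbation or no cost is handled.

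**The concern.** The objective is the effect of the vaccine on healthcare expenditure arising from exacerbations. The main way a preventive vaccine would lower that expenditure is by preventing exacerbations. The ratio in Protocol 8.1 cancels out exactly that component: numerator and denominator count the same events, so fewer events shrink both.

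A second problem appears if the ratio is formed patient by patient, as a rank or median test would ordinarily require. A patient with no exacerbation has zero events and zero cost, so no value exists. Comparing only patients with a defined value would mean comparing groups selected by a post-randomisation outcome, with more of the best-responding patients removed from the arm that works. An exacerbation with no recorded cost gives a division by zero; this is possible because the mildest grade in Protocol 5.6 can be managed without seeing a doctor.

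**Working it through.** The documents give no cost per exacerbation, no expected saving and no standard deviation, so there is no plan figure to reproduce.

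**Inputs**
- Decreases of 60% (active) and 30% (placebo), 90 patients per arm: Protocol 10.2 and SAP 7.1.1.
- Baseline of 3 exacerbations a year, range 2 to 4: an assumption, prompted by the entry criterion in Protocol 6.1 (three moderate events, or two with one hospitalised).
- Count dispersion k from 0 (Poisson) to 1 (negative binomial): an assumption.
- Cost per event with mean 1000 units and coefficient of variation 0.5 to 1.5, equal in both arms unless stated: an assumption.

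**1. Expected 12-month counts.** Placebo 3 × (1 − 0.30) = 2.1; active 3 × (1 − 0.60) = 1.2.

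**2. Algebra.** With E events at mean cost c, expenditure is E × c and the ratio is E / (E × c) = 1/c. E drops out.

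**3. Numbers.** Placebo: cost 2.1 × 1000 = 2100, ratio 2.1/2100 = 0.001. Active: cost 1.2 × 1000 = 1200, ratio 1.2/1200 = 0.001. Cost is (2100 − 1200)/2100 = 43% lower; the ratio is unchanged.

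**4. Patients with a 0/0 ratio.** P(no event) = exp(−m) for Poisson, and (1 + k·m)^(−1/k) for the negative binomial. At baseline 3, exp(−2.1) = 0.122 and exp(−1.2) = 0.301; with k = 1, 1/3.1 = 0.323 and 1/2.2 = 0.455.

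| Baseline | k | Placebo | Active | Undefined of 180 |
|---|---|---|---|---|
| 2 | 0 | 25% | 45% | 63 |
| 2 | 0.5 | 35% | 51% | 77 |
| 2 | 1 | 42% | 56% | 88 |
| 3 | 0 | 12% | 30% | 38 |
| 3 | 0.5 | 24% | 39% | 57 |
| 3 | 1 | 32% | 45% | 70 |
| 4 | 0 | 6% | 20% | 24 |
| 4 | 0.5 | 17% | 31% | 43 |
| 4 | 1 | 26% | 38% | 58 |

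These are 12-month shares. If the baseline-3 rates simply continued for the full 18 months, the means would be 2.1 × 1.5 = 3.15 and 1.2 × 1.5 = 1.8, and the Poisson shares exp(−3.15) = 4% and exp(−1.8) = 17%. The problem would be smaller, with the same imbalance.

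**5. Simulation** (baseline 3, 90 complete patients per arm, 2000 runs per scenario, k = 0, 0.5, 1, cost variation 0.5 and 1.5). A Mann-Whitney test at 0.05 on the per-patient ratio, undefined values omitted, rejected in 5% to 9% of runs. The same test on cost per patient, zeros kept, rejected in 63% to 99%.

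**6. Limit of the result.** If cost per event is also 30% lower on active (k = 0.5), the ratio test rejects in 100% of runs with cost variation 0.5 and 73% with 1.5. The ratio does respond to cheaper events.

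**7. The direct-cost comparison.** Costs with many zeros and a few hospital stays will be skewed, so the plan would use medians. In two rows of the table (baseline 2, k = 0.5 and 1), more than half of active patients have no event, so the active median is zero whatever the remaining patients cost. A median difference does not estimate the difference in mean expenditure, which is what determines the total.

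**The case against.** The strongest reply is that the ratio stands in one place only. Four other sections name plain expenditure, including the SAP's own endpoint list, and both documents compare direct costs between arms with an absolute effect and a 95% CI. That stands. A reader might infer from Protocol 8.1 that the trial cannot show a saving or leaves its cost objective unanswered; the documents do not support this. The direct-cost line answers the objective in part, and the remaining weakness is its default to medians for skewed data.

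A reader might also take the cost-benefit ratios to be the Protocol 8.1 ratio, computed per patient, with exacerbation-free patients left out. No section says so. The sentence speaks of ratios in the study groups, and a group ratio of totals is always defined when a group has costs. A permutation or bootstrap comparison of group ratios would also count as non-parametric. The per-patient reading is plausible but is an inference. What stands is that the quantity is undefined, and that a group-level version of the 8.1 ratio would still be the inverse of cost per event.

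Finally, the equality in step 3 follows from assuming equal cost per event. Reduced severity is itself a secondary objective, so a fall in cost per event is part of the hypothesis, and step 6 shows that the ratio would pick it up. It would be wrong to say that the ratio never moves. It is blind to avoided events as such.

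**Conclusion.** The concern holds in a limited form. One secondary outcome carries two incompatible definitions. The one in Protocol 8.1 measures the inverse of cost per exacerbation and gives no information on savings from avoided exacerbations. Taken per patient, it is undefined for an estimated 24 to 88 of 180 patients over 12 months, always more of them on active. These counts rest on the assumed baseline of 2 to 4 events, dispersion of 0 to 1, the plan's own effect and no dropout; the unchanged ratio rests on equal cost per event in both arms. The cost-benefit ratios in both documents cannot be computed without further definition. The planned comparison of direct costs means the objective is not lost, but as written it would probably report a median contrast where a mean is needed. The matter is worth correcting before analysis. It does not touch the primary outcome or its analysis.

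**What to change.** In Protocol 8.1, replace the ratio with total exacerbation-related expenditure per patient over the trial period, matching Protocol 5.1 and SAP 6.1.2. Enter exacerbation-free patients as zero. The trial period is 18 months per subject; the 12 treatment months may be reported separately, but should not silently replace it.

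In Protocol 10.1 and SAP 7.4.2, analyse this outcome as the between-arm difference in mean cost per patient with a bootstrap 95% CI, in place of the t test or Mood's median test. Delete the comparison of cost-benefit ratios. If a ratio is wanted, report one incremental ratio: difference in mean cost divided by difference in mean number of exacerbations.

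The cost is a change of wording in both documents. Table 1 already has resource consumption recorded at every visit, including months 15 and 18, so no new data are needed.

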## 8.2. Methods Used to Assess, Record, and Analyze the Efficacy Parameters

From the beginning of the trial, the subjects shall attend five scheduled visits (baseline visit, three follow-up visits, and the end of trial visit) with the study physician and unscheduled visits whenever their clinical condition warrants it.

During the baseline visit, the study doctor will conduct a detailed clinical interview during which the following will be recorded and performed:

- Screening of patients meeting the inclusion criteria.
- Signing of the informed consent form by the patient and the investigator.
- Collection of demographic data and ensuring that the patient will reside in the Autonomous Community of Madrid throughout the study period (September to May).
- Measurement and recording of vital signs (BP and HR).
- Collection of tobacco consumption data using the following formula: no. of cigarettes/day x no. of years/20 (baseline visit and visits 1, 2, 3, and 4).

- Testing for exhaled CO measure (all visits).
- Detailed medical history and general examination of the patient will be conducted, recording the data in the CRF (baseline visit and visits 1, 2, 3, and 4).
- Female subjects included in the study must provide a urine sample (first morning void) on which a pregnancy test will be performed based on a qualitative one-step chromatographic immunoassay (Acon) determining the presence of beta-human chorionic gonadotropin (beta-HCG). Subjects with a positive pregnancy test will not be included in the trial.
- Collection of blood from each subject (baseline visit, month 6, month 12, and end of trial visit at month 18) and analysis of the following parameters:
  - Complete blood count (flow cytometry).
  - Blood biochemistry, including basal blood glucose levels and liver function tests (enzymatic methods).
  - Viral serology testing: HCV, HBV, and HIV (ELISA serology).
  - General immunological parameters.
- All patients included in this trial will undergo a spirometry test during the baseline and end of trial visits (visits 4, at 12, 15, and 18 months from the start of the vaccination). Spirometry testing will be performed using the spirometer according to the protocol of the Respiratory Function Tests Unit of all hospitals participating in the trial.

[name]  
Traductor-Intérprete Jurado de INGLÉS  
Nº 9971

- Any concomitant medication will be recorded in the CRF during all visits.
- The healthcare resources consumption will be recorded during all visits using the CRF.
- The number of days of antibiotic treatment required will be recorded during visits 1-4 using the CRF.
- A visual analog scale will be scored by the subjects during all visits and the result will be recorded in the CRF.
- A visual analog scale will be scored by the investigator during all visits and the result will be recorded in the CRF.
- The CAT Quality-of-Life Questionnaire will be completed during all visits.
- The Patient Diary will be provided during visits 1-4.
- The Patient Diary will be collected during visits 2-4.
- The sublingual vaccine will be dispensed during visits 1-3.
- The sublingual vaccine will be collected during visits 2-4.
- The number of days of hospitalization due to a COPD exacerbation will be recorded during visits 1-4.
- The CRF will be used for this purpose.
- The adverse events occurred during the trial will be recorded during visits 1-4. The CRF will be used for this purpose.

- Any unscheduled visit required due to COPD exacerbations will be recorded during visits 1-4.
- The CRF and CRF of unscheduled visits will be used for this purpose.
- The patients who dropped out from the trial during its course and the cause for the dropout will be recorded during visits 1-4. The CRF will be used for this purpose.
- Any observation deemed appropriate about any aspect of the trial will be recorded in the CRF during all visits.
- The trial monitor will review the CRF during all visits.

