## 5. TRIAL DESIGN

### 5.1. Description of the Primary and Secondary Outcome

- **Primary outcome:**

- The primary efficacy outcome is a decrease in the mean number of COPD exacerbations. A clinical diagnosis of an exacerbation according to the GOLD definition will be considered; that is, an event occurring throughout the natural course of the disease, characterized by a change of acute onset, beyond the daily variability, in the patient's dyspnea, cough, and/or expectoration, which may require a change in the patient's usual medication.

- **Secondary outcomes:**

- Decrease in the rate of COPD exacerbations per study group at 12 months (end of the trial treatment) and 6 months after the trial's termination (follow-up).
- Decrease in the severity of the COPD exacerbations. The severity of the exacerbations will be measured based on the consumption of healthcare resources (i.e., visits to the Emergency Department, hospitalizations, or consultations), as follows:
  - ICU hospitalization: 4 points.
  - Standard hospitalization: 3 points.
  - Emergency Department visit: 2 points.
  - Consultation involving a change in the patient's usual treatment: 1 point.

[name]  
Traductor-Intérprete Jurado de INGLÉS  
Nº 9971

- Time elapsed between the start of the treatment and the first COPD exacerbation.
- Use of drugs (antibiotics, corticosteroids, etc). Drug consumption will be scored as follows:
  - Use of antibiotics: 1 point.
  - Use of inhaled corticosteroids: 2 points.
  - Use of systemic corticosteroids: 3 points.
  - Use of oxygen therapy: 4 points.
  - Use of mechanical ventilation: 5 points.
- Number of hospitalizations due to COPD exacerbations.
- Days of hospitalization due to COPD exacerbations.
- Number of visits to the Emergency Room.
- Number of unscheduled medical consultations due to COPD exacerbations.
- Health-related quality of life, as determined by an adapted version of the specific CAT test.
- Healthcare expenditure resulting from resource consumption during episodes of COPD exacerbations occurring during the trial period.
- Variations (change between the baseline level and months 0, 3, 6, and 12, as well as in comparison with the placebo) in the following immunological parameters in the patients participating in the immunological substudy (N = 60) and/or those of the subgroup of the induced sputum study (N = 20) (between month 0 prior to the administration of the vaccine and month 12).

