### **9.3. Procedures for Recording and Reporting Adverse Events and Intercurrent Diseases, and for Submitting their Reports**

All events meeting the definition of an adverse event should be collected and recorded between the start of the first trial-related activity (after the subject's signature of the informed consent) and the end of the post-treatment follow-up period required by the protocol. Subjects will be questioned whether they noticed any adverse event during each visit to the site. All adverse events, whether observed by the investigator or reported by a subject, should be recorded in the corresponding section of the case report form and evaluated by the investigator.

The minimum information to be specified shall be the description, severity, duration, temporal sequence, and method of detection of the adverse event. The treatment administered to manage the event must also be specified.

The investigator shall immediately report all serious adverse events and/or suspected unexpected serious adverse events (SUSARs), regardless of their relation to the investigational medicinal product, by telephone ( [REDACTED] ) or fax ( [REDACTED] ), to the staff of Inmunotek's Medical Department (always within the first 24 hours of their onset). The initial and follow-up reports shall identify the trial subjects by a unique identification code assigned to each one of them.

[name]  
Traductor-Intérprete Jurado de INGLÉS  
Nº 9971

The regulations in force will be followed when issuing the safety information notification to the Health Authorities, the Research Ethics Committees, and the investigators.

If a suspected unexpected serious adverse reaction occurs within the context of a double-blind clinical trial, the treatment code of the particular subject must be disclosed for reporting purposes. Whenever possible, blinding should be maintained for the investigator and the persons responsible for the analysis and interpretation of the results, as well as for drafting the study conclusions.

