4.1. Study Assessments

Table 1 shows procedures to be followed during the study.

Table 1 Overview of the Trial Design, Procedures, and stages

VISIT No.	Baseline	1	2	3	4	5	6
		0	3	6	12	15	18
Period window		±10 days					
Informed consent	✓						
Inclusion/exclusion criteria	✓						
Demographic data (including area of residence)	✓						
Vital signs (BP and HR)	✓						
Tobacco consumption (no. of cigarettes/day ✓ no. of years/20)	✓	✓	✓	✓	✓	✓	✓
Medical history/complete examination	✓	✓	✓	✓	✓	✓	✓
Exhaled CO	✓	✓	✓	✓	✓	✓	✓
Hematology	✓			✓	✓		✓
Serum chemistry	✓			✓	✓		✓
Viral serology testing (HBV, HCV, and HIV)	✓				✓		✓
Complete immunological evaluation	✓			✓	✓		✓
Immunological substudy (N = 60)		✓	✓	✓	✓		✓
Immunological substudy with induced sputum (N = 20)		✓			✓		
Spirometry	✓				✓	✓	✓
Recording of concomitant medication	✓	✓	✓	✓	✓	✓	✓
Pregnancy test	✓						
Recording of healthcare resource consumption	✓	✓	✓	✓	✓	✓	✓
Randomization no.		✓					
No. of days of antibiotic treatment required		✓	✓	✓	✓	✓	✓
Subject's visual analog scale score	✓	✓			✓	✓	✓
Investigator's visual analog scale score	✓	✓			✓	✓	✓

Quality of life questionnaire	✓	✓	✓	✓	✓	✓	✓
Provision of the patient diary		✓	✓	✓	✓		
Collection of the patient diary			✓	✓	✓		
Delivery of the sublingual vaccine		✓	✓	✓			
Collection of the sublingual vaccine			✓	✓	✓		
Recording of the no. of days of hospitalization		✓	✓	✓	✓	✓	✓
Recording of adverse events		✓	✓	✓	✓	✓	✓
Recording of unscheduled visits		✓	✓	✓	✓	✓	✓
Recording of trial dropout/termination cause		✓	✓	✓	✓		
Comments	✓	✓	✓	✓	✓	✓	✓
CRF review	✓	✓	✓	✓	✓	✓	✓

5. Trial Population

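### Protocol 8.2 stops recording of four items at visit 4 (month 12) and counts five visits, contradicting Table 1 and the sections that require data to month 18

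*Protocol*

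**What the plan says.** Protocol 8.2, the section on how efficacy data are assessed and recorded, says that "the subjects shall attend five scheduled visits (baseline visit, three follow-up visits, and the end of trial visit"). It then limits four items to visits 1-4:

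- Adverse events: "The adverse events occurred during the trial will be recorded during visits 1-4".
- Hospital days: "The number of days of hospitalization due to a COPD exacerbation will be recorded during visits 1-4".
- Antibiotic days: "The number of days of antibiotic treatment required will be recorded during visits 1-4 using the CRF".
- Unscheduled visits: "Any unscheduled visit required due to COPD exacerbations will be recorded during visits 1-4".

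Table 1 (protocol 5.2.1 and SAP 4.1) has a baseline visit and visits 1-6 at months 0, 3, 6, 12, 15 and 18, and marks all four items at visits 1-6. Protocol 9.3 has adverse events collected from consent to "the end of the post-treatment follow-up period required by the protocol". Protocol 5.1 lists as a secondary outcome "Decrease in the rate of COPD exacerbations per study group at 12 months (end of the trial treatment) and 6 months after" the trial's end.

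**The concern.** Section 8.2 reads as an operative recording instruction, so a site or a CRF designer could reasonably work from it. Read literally, it ends the recording of these items at the end of treatment, just where the post-treatment outcome begins.

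Three of the four items are main routes by which an exacerbation after month 12 would reach the database, since Table 1 has no row for exacerbations as such. Adverse event reporting cannot replace them, because protocol 9.1 excludes COPD exacerbations from adverse events.

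The analysis risk is that a missing record looks like a zero. If some sites recorded to month 18 and others stopped at month 12, a patient with no entries at visits 5 and 6 may have had no exacerbation or may have had none written down. SAP 7.1.2 imputes nothing, and the Poisson model in SAP 7.4.1 takes length of follow-up as exposure. A patient seen at month 18 but recorded only to month 12 would bring 18 months of exposure and 12 months of events.

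**Working it through.** **Visit count.** The parenthesis in 8.2 gives 1 baseline + 3 follow-up + 1 end-of-trial = 5, which equals baseline plus visits 1-4. Table 1 gives 1 + 6 = 7. The difference is visits 5 and 6 (months 15 and 18). If the end-of-trial visit in that parenthesis is instead read as month 18, as the blood-sampling line of 8.2 calls it, five visits still do not fill the seven columns.

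**Recording windows side by side.**

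| Item | Protocol 8.2 | Table 1, protocol and SAP | Elsewhere in the protocol |
|---|---|---|---|
| Scheduled visits | 5 | 7 | 5.5: clinical response also recorded 3 and 6 months after treatment |
| Adverse events | visits 1-4 | visits 1-6 | 9.3: consent to end of follow-up |
| Hospital days | visits 1-4 | visits 1-6 | 5.2.1: during immunization and the 6 months after it |
| Antibiotic days | visits 1-4 | visits 1-6 | 5.2.1: recorded until remission, no visit limit |
| Unscheduled visits | visits 1-4 | visits 1-6 | 5.2.1: allowed whenever the disease worsens, no visit limit |

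**Section 8.2 against itself.** The same section schedules spirometry at months 12, 15 and 18 and blood at month 18, so it cannot describe a trial that ends at month 12.

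**Which analyses need months 12-18.** They are the secondary outcome on the post-treatment rate (protocol 5.1, SAP 6.1.2); first and any exacerbation over the whole study in the ITT and PP sets (SAP 7.4.2); whole-study exacerbation counts, which SAP 7.4.2 lists only for the COPD-severity populations; and all adverse events of the trial (SAP 7.5). ITT and PP exacerbation counts stop at month 12 and do not depend on these data.

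**Size if 8.2 is followed.** The uncovered time is 18 − 12 = 6 months, and 6/18 = 33% of planned observation per patient. Let f be the share of patients at sites that stopped these items at month 12. The documents do not give f, so it is shown over its full range. Assume a constant event rate, full 18-month exposure and no recovery from other records. The fraction of events recorded is then

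- post-treatment window: 1 − f
- whole study: (18 − 6f)/18 = 1 − f/3

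| f | Post-treatment events recorded | Whole-study events recorded |
|---|---|---|
| 0 | 100% | 100% |
| 0.5 | 50% | 83% |
| 1 | 0% | 67% |

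These figures are upper bounds on the loss, because they ignore the backup records discussed below.

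**The case against.** The strongest reply is that 8.2 is the outlier and the protocol's intent is clear. Both schedules, 5.2.1, 5.5 and 9.3 all run to month 18, and 8.2 itself brings patients back at months 15 and 18. Adverse events are governed by section 9: 9.1 requires all of them during the trial, and 9.3 has patients asked about them at each visit. Section 8.2 also records healthcare resource use and concomitant medication at every visit, and the severity score in 5.1 is built from resource use. Nothing in the documents shows that any site or CRF page followed 8.2.

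Most of this stands, and it limits the point. A reader might infer that no events or adverse events exist after month 12. The documents do not support that, because the adverse event duty stands independently and part of the exacerbation-related use would be captured anyway. What remains is that the four recording instructions in 8.2 are wrong as written, and that resource and medication records are only a partial substitute for dated unscheduled visits, hospital days and antibiotic days.

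A reader might also infer that withdrawals in months 12-18 go unrecorded, since the Table 1 row "Recording of trial dropout/termination cause" is marked only at visits 1-4. That does not follow either. Protocol 6.3.1 requires the cause and date of every dropout or withdrawal in the CRF, and 6.3.2 requires their timing, neither with a visit limit. Section 8.2 and both tables also agree with each other on that row.

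**Conclusion.** The contradiction is real and can be seen by setting the texts side by side: five visits against seven, and month 12 against month 18 for four items. It should be corrected.

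Its consequence is conditional. Only where a site followed 8.2 over Table 1 would these items be missing for 6 of 18 months. In that case the post-treatment rate would rest on partial backup records, and whole-study rates would be understated by at most one third under the constant-rate assumption. The recording rule does not depend on treatment arm and the trial is double-blind, so the text gives no reason to expect a loss that favours one arm. The expected harm is understated rates and lost precision after month 12.

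The sample size in protocol 10.2 rests on exacerbations during the 12 months of treatment, and that count is untouched.

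**What to change.** In protocol 8.2, state seven scheduled visits (baseline plus visits 1-6) and change visits 1-4 to visits 1-6 for adverse events, antibiotic days, exacerbation hospital days and unscheduled visits, so that the section matches Table 1. The lines in 8.2 on tobacco consumption and on medical history and examination also stop at visit 4 where Table 1 continues to visit 6, and can be aligned in the same edit.

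Before database lock, list by site, blinded to arm, whether the four items were recorded at months 15 and 18 for each patient who attended. Where they were not recorded, treat months 12-18 as unobserved for the exacerbation analyses instead of as event-free, and end that patient's exposure at the last visit with recording.

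The wording change costs a few lines and needs no new visits, since Table 1 already schedules visits 5 and 6. The CRF is not among the documents, so the site listing should also confirm that its pages for those visits carry the four items.
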